6.14.1.3. Patient-reported Outcomes

Patient-reported outcomes will be assessed through surveys. Medication satisfaction will be measured by the HIV Treatment Satisfaction Questionnaire (HIVSTQ) adapted for PrEP and PrEP stigma will be measured by the PrEP Stigma Scale at months 1, 5, and 11. PrEP acceptance will be measured by the Modified Injection Treatment Acceptance Questionnaire (Modified I-TAQ) at months 3, 9, and 12. Barriers to adherence to oral PrEP and reasons for PrEP discontinuation will be assessed through brief behavioral surveys every month after the initiation of PrEP. Barriers to adherence to CAB-LA injections and reasons for PrEP discontinuation will be assessed through brief behavioral surveys at months 1, 3, 5, 7, 9, and 11.

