
Why are you using pre-exposure prophylaxis (PrEP) to prevent HIV? [Select all that apply]
  Reduce acquisition of HIV from sex  Reduce acquisition of HIV from IV drug use	7

The next 5 questions ask about your food, housing, and transportation routines from the past 12 months. If you have concerns and need support, please check in with your provider at your next visit or call 2-1-1 for immediate support.
	

In the last 12 months, was there a time when you were not able to pay the mortgage or rent on time?
  No  Yes  Not applicable	8

In the last 12 months, was there a time when you did not have a steady place to sleep or slept in a shelter (including now)?
  No  Yes	9

In the last 12 months, have you or the people you live with been unable to get utilities (heat, electricity) when it was really needed?
  No  Yes	10

Within the past 12 months, the food you bought just didn't last and you didn't have money to get more.
  Never true  Sometimes true  Often true	11

Within the past 12 months, has lack of transportation kept you from medical appointments, getting your medicines, non-medical meetings or appointments, work, or from getting things that you need?
  No  Yes	12

Do you feel physically and emotionally safe where you currently live?
  Yes  No	13

During the past 30 days, have you used any of the following?
 
 • An illegal drug (such as by snorting it or injecting it) • Pain killer to get high (like OxyContin, sometimes called Oxy or OC) or Percocet (sometimes called Percs) • Prescription drugs not prescribed to you  No  Yes	14

People who experience discrimination may be at higher risk of negative health outcomes. Sharing your experiences with discrimination in everyday life and in healthcare settings may help researchers learn how to reduce negative health outcomes associated with discrimination.
	

The next 3 statements describe how others may treat you.	
In your day-to-day life, how often do any of these happen to you?	

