You are treated with less respect than other people are. 
  Never  Less than once a year  A few times a year  A few times a month  At least once a week  Almost every day 	15
People act as if they're better than you. 
  Never  Less than once a year  A few times a year  A few times a month  At least once a week  Almost every day 	16
What do you think is the main reason for these experiences? (Select 1) 
  Your gender  Your sexual orientation  Your race  Your religion  Some aspect of your physical appearance  Your education or income level  Other: [Write in] 	17

End Message: Thank you for completing this survey!

Persistence Assessment

Activity Title: Are You Still Taking PrEP?

Activity Description: In this short survey, we'll ask you some questions about your PrEP journey and any challenges you may have encountered.

Activity:

1. Are you still getting PrEP medicine by an injection from your healthcare provider?

- Yes, I am taking PrEP ([branching logic to question 4](#))
- No, I stopped taking PrEP ([branching logic to question 2](#))

2. If you stopped taking PrEP, which of the following best describes the reason(s) why?

[Select up to 2]

- I no longer feel I needed to take PrEP ([branching logic to question 3 if selected](#))
- It was too difficult to take to take PrEP as prescribed with my lifestyle
- I felt I was being judged by others for taking PrEP
- I experienced side effects from taking PrEP

- I take too many medications
- There were too many appointments as part of my PrEP care
- I tested positive for HIV
- Other: [Fill in the blank]

3. Which of the following best describes why you no longer feel you need to take PrEP?

- I am no longer having sex
- I am in a monogamous relationship
- I am no longer using injectable drugs
- My partners and I are all regularly using condoms and getting tested for HIV
- Other: [Fill in the blank]

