4. If you are still taking PrEP, what challenges have you experienced?

- Have not experienced any challenges
- Keeping up with clinical visits and laboratory testing
- Concerns about side effects
- Finding transportation to my appointments
- Stigma or discrimination from family, friends, or partner(s)
- Stigma or discrimination from healthcare professionals
- Other: [Fill in the blank]

5. Did a healthcare provider (for example, a doctor, nurse or pharmacist) or navigator ever ask you what may make it difficult for you to take PrEP? (Month 1 & 11)

- Yes
- No
- Unsure

Activity Type: Patient Reported Outcomes – Set 1

Activity Title: Your Experiences With PrEP

Activity Description: This month we'll ask you to answer questions about your experience using PrEP and your thoughts about PrEP-related stigma. We'll also ask some questions about your experience using this mobile app to support you taking PrEP. The survey is 3 parts with a total of 24 questions. It should take you 10-15 minutes to complete.

Activity:

Part 1. Tell us about your experience using PrEP

The following questions are related to the PrEP medicine you use to protect you from HIV infection and your experience over the **past 4 weeks**. Please answer each question by selecting a number on each of the scales.

1. How satisfied are you with your **current medicine** for PrEP?
 - Very satisfied
 - Satisfied

- Neither satisfied or dissatisfied
 - Dissatisfied
 - Very dissatisfied
2. How **bothered** are you by **any side effects** from the medicine you use for PrEP?
- Very unbothered
 - Unbothered
 - Neither unbothered or bothered
 - Bothered
 - Very bothered
 - I have not experienced any side effects in the last 4 weeks
3. How satisfied are you with the **convenience** of PrEP recently?
- Very satisfied
 - Satisfied
 - Neither satisfied or dissatisfied
 - Dissatisfied
 - Very dissatisfied
4. How satisfied are you with the **discreetness** of PrEP recently?
- Very satisfied
 - Satisfied
 - Neither satisfied or dissatisfied
 - Dissatisfied
 - Very dissatisfied
5. How satisfied are you with your **understanding of using PrEP** to prevent HIV?
- Very satisfied
 - Satisfied
 - Neither satisfied or dissatisfied
 - Dissatisfied
 - Very dissatisfied
6. How satisfied are you with the extent to which PrEP **fits in with your lifestyle**?
- Very satisfied
 - Satisfied
 - Neither satisfied or dissatisfied
 - Dissatisfied
 - Very dissatisfied

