5. If you are still taking PrEP, what challenges have you experienced? [Select up to 2]

- Have not experienced any challenges
- Remembering to take PrEP every day
- Keeping up with clinical visits and laboratory testing
- Concerns about side effects
- Finding transportation to my appointments
- Stigma or discrimination from family, friends, or partner(s)
- Stigma or discrimination from healthcare professionals
- Other: [Fill in the blank]

6. Did a healthcare provider (for example, a doctor, nurse, or pharmacist) or navigator ever ask you what may make it difficult for you to take PrEP?

- Yes
- No
- Unsure

End Message: Thank you for completing this survey!

Patient Reported Outcomes – Set 1

Activity Title: Your Experiences with PrEP

Activity Description: This month we'll ask you to answer questions about your experience using PrEP and your thoughts about PrEP-related stigma. We'll also ask some questions about your experience using this mobile app to support you taking PrEP. The survey is 3 parts with a total of 24 questions. It should take you 10-15 minutes to complete.

Activity:

Part 1. Tell us about your experience using PrEP

The following questions are related to the PrEP medicine you use to protect you from HIV infection and your experience over the **past 4 weeks**. Please answer each question by selecting a number on each of the scales.

1. How satisfied are you with your **current medicine** for PrEP?
 - Very satisfied
 - Satisfied
 - Neither satisfied or dissatisfied
 - Dissatisfied
 - Very dissatisfied
2. How **bothered** are you by any **side effects** from the medicine you use for PrEP?
 - Very unbothered
 - Unbothered
 - Neither unbothered or bothered
 - Bothered
 - Very bothered
 - I have not experienced any side effects in the last 4 weeks
3. How satisfied are you with the **convenience** of PrEP recently?
 - Very satisfied
 - Satisfied
 - Neither satisfied or dissatisfied
 - Dissatisfied
 - Very dissatisfied
4. How satisfied are you with the **discreetness** of PrEP recently?
 - Very satisfied
 - Satisfied
 - Neither satisfied or dissatisfied
 - Dissatisfied
 - Very dissatisfied
5. How satisfied are you with your **understanding of using PrEP** to prevent HIV?
 - Very satisfied
 - Satisfied

- Neither satisfied or dissatisfied
- Dissatisfied
- Very dissatisfied
6. How satisfied are you with the extent to which PrEP **fits in with your lifestyle?**
- Very satisfied
- Satisfied
- Neither satisfied or dissatisfied
- Dissatisfied

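### Transportation and stigma from healthcare professionals are tick options for people still on PrEP but are not named as reasons for stopping, so they are likely to be under-counted as stop reasons

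*Combined protocol and SAP*

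**What the plan says.** Secondary objective 2 includes reasons for PrEP discontinuation. Section 6.14.1.3 makes the brief surveys the instrument for it: "Barriers to adherence to CAB-LA injections and reasons for PrEP discontinuation will be assessed through brief behavioral surveys". It says the same for the oral arm, at monthly intervals.

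In the CAB-LA form (Appendix B), the first question splits participants. Those who answer "Yes, I am taking PrEP" are sent to Q4, and those who answer "No, I stopped taking PrEP" are sent to Q2.

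- Q2 asks "If you stopped taking PrEP, which of the following best describes the reason(s) why" and allows up to two answers. Its named reasons concern need, lifestyle, being judged by others, side effects, number of medications, number of appointments and a positive HIV test. A write-in Other follows.
- Q4 opens "If you are still taking PrEP, what challenges have you experienced". Its options include "Finding transportation to my appointments" and stigma from healthcare professionals.

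The oral form (Appendix C) is built the same way. Its stop-reason item is Q3. Its challenges item is Q5, which carries the transportation option and "Stigma or discrimination from healthcare professionals".

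The plan treats transportation as a possible barrier elsewhere. Baseline survey Q12 asks every participant whether, over the past year, it "has lack of transportation kept you from medical appointments, getting your medicines" or other things they needed. The clinician surveys in Appendix D list patient transportation among the barriers to CAB-LA (baseline item 8, follow-up item 17).

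**The concern.** The two barriers are offered as tick boxes to people who are managing to stay on PrEP and withheld from people who are explaining why they left. A named option is easier to choose than a blank field, so the same barrier is likely to be recorded less completely in stoppers than in continuers.

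What is at stake is a named secondary outcome: the table of reasons for stopping, and any statement comparing the barriers of those who stopped with those who continued. Stoppers may be few, and reasons not offered at the time of stopping are hard to recover later.

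**Working it through.** No figure in the plan bears directly on this point. Its one sample-size figure, the interval in section 7, concerns adherence. It reproduces: 0.90 − 0.65 = 0.25; standard error √(0.90 × 0.10/70 + 0.65 × 0.35/35) = 0.0882; 0.25 ± 1.96 × 0.0882 gives 0.0771 to 0.4229. The point does not depend on it. The check is a comparison of option lists.

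| Item | Answered for | Transportation named | Stigma from healthcare professionals named | Write-in Other |
|---|---|---|---|---|
| Appendix B Q2 | CAB-LA participants who stopped | No | No | Yes |
| Appendix C Q3 | Oral participants who stopped | No | No | Yes |
| Appendix B Q4 | CAB-LA participants still taking PrEP | Yes | Yes | Yes |
| Appendix C Q5 | Oral participants still taking PrEP | Yes | Yes | Yes |
| Appendix D follow-up item 20 | Clinicians, about CAB-LA participants who stopped | No | No | No |

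Each of the three stop-reason lists has seven named reasons. Neither barrier is among them: 0 of 7 in each.

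**Routing.** In Appendix B the branching sends stoppers to Q2 and continuers to Q4. In Appendix C the printed branch numbers do not match the numbered questions: continuers are sent to question 4, but the challenges item is Q5. For the oral arm the argument therefore rests on the opening condition of Q5, which limits it to people still taking PrEP.

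**Where a stopper's answer can go.** There are two routes. One is the write-in. The other is a neighbouring option: number of appointments (or difficulty with lifestyle or schedule) for transportation, and being judged by others for clinician stigma. The second route keeps part of the signal but loses its source. Having too many visits is not the same as being unable to reach them, and being judged by others does not identify clinic staff.

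**Size.** Let N be the number of stoppers, b the share who stopped because of the barrier, and w the share of those who write it in. The number recorded under its own name is N × b × w. The fraction captured is w, and the count is complete only if w = 1. The documents give neither b nor w, and give no persistence rate. For illustration only, borrow the plan's 0.90 adherence figure as persistence, so N = 70 × 0.10 = 7, and assume b = 0.30. Then 7 × 0.30 = 2.1 stoppers are expected to have the barrier. The number recorded is 0, 0.5, 1.1, 1.6 or 2.1 for w = 0, 25%, 50%, 75% or 100%. For b from 0.10 to 0.50 the expected number runs from 0.7 to 3.5, and the number recorded runs from 0 up to that value. This shows the direction of the error but does not estimate it.

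**The case against.** The case on the other side is substantial, and most of it stands as mitigation.

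- **The survey is repeated.** Section 6.2 schedules it at months 1, 3, 5, 7, 9 and 11 for CAB-LA and monthly for oral PrEP. Someone who ticks transportation at month 3 and reports stopping at month 5 is a stopper with a recorded transportation barrier. A reader might infer that every ticked transportation barrier belongs to someone who stayed on PrEP. It shows only that the person was on PrEP when answering.
- **Baseline Q12 is asked of everyone.** Under section 7, variables associated with persistence in univariate analysis enter the multivariate models, so transportation can be related to persistence directly. A reader might infer that the data will suggest transportation does not cause stopping. The documents do not support that.
- **Two answers and a write-in are allowed.** A stopper can tick a near option and also write in transportation. With few stoppers, each free-text answer can be read and coded.
- **Other items carry related information.** PRO Set 1 asks about unfair treatment by doctors, and clinician item 17 lets staff report transportation as an observed barrier.

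A reader might also infer that transportation is the main drawback of CAB-LA. The clinician lists give it as one barrier among several, unranked.

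What these replies leave untouched is that none of these sources is a stop reason. A baseline difficulty, or a challenge ticked while continuing, does not say why the person later stopped. The write-in closes the gap only if everyone affected uses it.

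**Conclusion.** The point holds as a modest defect in a secondary, descriptive outcome. The option lists are as shown in both arms and in clinician item 20. As stop reasons, the two barriers can be recorded under their own names only by write-in from the patient, and not at all in clinician item 20. They are likely to be under-counted. That conclusion assumes only that some affected stoppers would tick a named option but would not write one in. The amount cannot be computed from the documents. Barriers also cannot be compared like for like between stoppers and continuers, because the two groups choose from different lists.

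The stigma half is weaker than the transportation half: the option about being judged by others can absorb it, so what is lost is mainly the source. The persistence and adherence comparisons and the sample size are not affected.

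**What to change.** 1. Add the transportation and healthcare-professional stigma options to the stop-reason items (Appendix B Q2, Appendix C Q3), in the wording already used in the challenges items.
2. Add a transportation option and an Other write-in to clinician follow-up item 20.
3. Optionally, show the challenges item once to anyone who reports stopping, reworded to refer to the time before they stopped, so that both groups answer the same barrier list.

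The cost is a text change in two app forms and one clinician item, and a slightly longer option list (plus one extra question for stoppers if the third step is taken). Visits and sample size do not change.

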6. STUDY INTERVENTIONS AND PROCEDURES

6.1. Study Procedures and Interventions Table (Figure 6a)

CAB-LA PrEP Arm (N=70)													
Month 0	Month 0	Month 1	Month 2	Month 3	Month 4	Month 5	Month 6	Month 7	Month 8	Month 9	Month 10	Month 11	Month 12
Baseline labs and 1 st PrEP injection Baseline demographic survey	Baseline evaluation and introduction to support group	2 nd PrEP injection Persistence Assessment PRO data collection – Set #1	Education modules and health literacy evaluation	Follow-up labs and 3 rd PrEP injection PRO data collection – Set #2 Persistence Assessment	Education modules and health literacy evaluation	Follow-up labs and 4 th PrEP injection Persistence Assessment PRO data collection – Set #1	Education modules and health literacy evaluation	Follow-up labs and 5 th PrEP injection Persistence Assessment	Education modules and health literacy evaluation	Follow-up labs and 6 th PrEP injection PRO data collection – Set #2 Persistence Assessment	Education modules and health literacy evaluation	Follow-up labs and 7 th PrEP injection Persistence Assessment PRO data collection – Set #1	PRO data collection – Set #2
Oral PrEP Arm (N=35)													
Month 0	Month 0	Month 1	Month 2	Month 3	Month 4	Month 5	Month 6	Month 7	Month 8	Month 9	Month 10	Month 11	Month 12
Baseline labs and PrEP prescription filled Baseline demographic survey	Baseline evaluation and introduction to support group	Persistence Assessment PRO data collection – Set #1	Education modules and health literacy evaluation Persistence Assessment	Follow-up labs and PrEP prescription refill PRO data collection – Set #2 Persistence Assessment	Education modules and health literacy evaluation Persistence Assessment	Persistence Assessment PRO data collection – Set #1	Follow-up labs and PrEP prescription refill Education modules and health literacy evaluation Persistence Assessment	Persistence Assessment	Education modules and health literacy evaluation Persistence Assessment	Follow-up labs and PrEP prescription refill PRO data collection – Set #2 Persistence Assessment	Education modules and health literacy evaluation Persistence Assessment	Persistence Assessment PRO data collection – Set #1	Follow-up labs and PrEP prescription refill PRO data collection – Set #2 Persistence Assessment

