6.2. Description of Study Procedures

Before any screening procedure is performed, informed consent will be obtained. Labs will be taken at baseline and months 3, 5, 7, 9, and 11 for the CAB-LA cohort and at baseline and months 3, 6, 9, and 12 for the Oral PrEP cohort (only collected through standard of care). Participants will complete a baseline evaluation and be introduced to a support group at baseline. Patients will complete assessments within the TheraPay App. Clinicians will complete assessments outside of the app. Patients in both cohorts will complete baseline demographic surveys in month 0, patient reported outcomes (PRO) data collection set 1 in months 1, 5, and 11 and PRO data collection set 2 in months 3, 9, and 12. Patients in the CAB-LA PrEP cohort will complete persistence assessments in months 1, 3, 5, 7, 9, and 11. Patients in the Oral PrEP cohort will complete persistence assessments every month from months 1 through 12. Clinic staff will complete surveys at baseline, month 6, month 12, and at the end of the study. The

schedule of assessments for the CAB-LA PrEP cohort, Oral PrEP cohort, and clinicians is presented in figure 6a. Instruments are in Appendix B for the CAB-LA cohort, in Appendix C for the Oral PrEP cohort, and Appendix D for clinicians. Patient incentives for completing the assessment activities are outlined in Appendix E.

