6.13. Interventions: PrEP Initiation and Digital Health Companion Program

6.13.1. Participants will be enrolled in the CAB-LA and Oral PrEP cohorts. Participants in the CAB-LA cohort will receive their first dose of the PrEP injection at month 0. Injections will also be administered in months 1, 3, 5, 7, 9, and 11. Participants in the Oral PrEP cohort will have their prescription filled at month 0, 3, 6, 9, and 12. The schedule of dosing is presented in Figure 6a.

6.13.2. Participants in both cohorts will complete education modules and health literacy evaluations in the TheraPay App in months 2, 4, 6, 8, and 10 as presented in Figure 6a. Education Modules include PrEP Medicines (month 2), Protecting Yourself from HIV, STIs, and other infections (month 4), Building a Support System for HIV Prevention Month 6: Being an Active Participant in Your Own Care (month 8), and Overcoming Stigma and Becoming a Health Advocate (month 10).

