End Message: Thank you for completing this survey! We will ask you these same questions again later to see how your responses have changed.

Patient Reported Outcomes – Set 2

Activity Title: Your Experiences With PrEP

Activity Description: This month we'll ask you to answer questions about your experience using PrEP (pre-exposure prophylaxis). We'll also ask some questions about your experience using this mobile app to support you taking PrEP. The survey is two parts with a total of 16 questions. It should take you 8-12 minutes to complete.

Part 1. Tell us about your experience using PrEP

Question	Question # CAB LA Arm [14]	Sub-concept
Over the past 4 weeks, how confident were you that PrEP prevented you from acquiring HIV ?  Very confident  Quite confident  Somewhat confident  A little confident  Not at all confident	1	Perceived efficacy
[CAB-LA arm] Over the past 4 weeks, did you experience any side effects, including injection site side effects (such as redness, bruising, or swelling) from the PrEP injection?  No (branching logic to question 5)  Yes (branching logic to show 3)	2	Acceptance of side effects
Over the past 4 weeks, how acceptable or unacceptable did you find the side effects from PrEP?  Very acceptable  Acceptable  Neither acceptable or unacceptable  Unacceptable  Very unacceptable	3 (branching logic)	Acceptance of side effects
Over the past 4 weeks, did the side effects of the PrEP medication interfere with your physical activity (such as lifting things, walking, jogging), your leisure or free time activities (such as gardening, reading, dancing, visiting friends), or your daily activities (such as shopping, working, house work, yard work)?  No, not at all  Yes, a little  Yes, somewhat  Yes, quite a bit  Yes, very much	4 (branching logic)	Acceptance of side effects
[CAB LA arm] Over the past 4 weeks, did you experience any pain when getting your PrEP injection?	5	Acceptance of side effects

 No (branching logic to question 7)  Yes (branching logic to question 6)		

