
[CAB LA arm] Over the past 4 weeks, how acceptable or unacceptable did you find the pain you experienced when getting your PrEP injection?
  Very acceptable  Acceptable  Neither acceptable or unacceptable  Unacceptable  Very unacceptable	6 (branching logic)	Acceptance of side effects

[CAB LA arm] Over the past 4 weeks, how acceptable or unacceptable did you find the time it took to get the PrEP injection at your doctor's office?
  Very acceptable  Acceptable  Neither acceptable or unacceptable  Unacceptable  Very unacceptable	7	Convenience

[CAB LA arm] Over the past 4 weeks, how acceptable or unacceptable did you find the number of times you had to get your PrEP injection?
  Very acceptable  Acceptable  Neither acceptable or unacceptable  Unacceptable  Very unacceptable	8	Convenience

[CAB LA arm] Over the past 4 weeks, how easy or difficult was it to remember to go to your appointments for your PrEP injection?
  Very easy  Easy  Neither easy or difficult  Difficult  Very difficult	9	Convenience

[CAB LA arm] Over the past 4 weeks, how easy or difficult was it to fit in getting the PrEP injection into your daily life?
 
  Very easy  Easy  Neither easy or difficult  Difficult  Very difficult 	10	Convenience

Over the past 4 weeks, did you ever feel like you needed to hide your attendance to PrEP injection appointments so others would not see you?
 
  No, not at all  Yes, occasionally  Yes, often  Yes, quite often  Yes, all the time 	11	Convenience

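### CAB-LA acceptance survey (PRO Set 2): the injection items use a 4-week recall with no 'no injection' answer, although the survey can fall outside 4 weeks of an injection

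*Combined protocol and SAP*

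**What the plan says.** **Injection schedule.** Section 6.13.1: "Participants in the CAB-LA cohort will receive their first dose of the PrEP injection at month 0", and then "Injections will also be administered in months 1, 3, 5, 7, 9, and 11". There is none at month 12.

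**Survey schedule.** Section 6.2 places "PRO data collection set 2 in months 3, 9, and 12" in both cohorts. Section 6.14.1.3 agrees: "PrEP acceptance will be measured by the Modified Injection Treatment Acceptance Questionnaire (Modified I-TAQ) at months 3, 9, and 12".

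**The items.** Appendix B, PRO Set 2, Part 1, item 5 reads "Over the past 4 weeks, did you experience any pain when getting your PrEP injection". Its negative answer carries the instruction "No (branching logic to question 7", which bypasses item 6, on how acceptable the pain was. Item 7 asks, over the same 4 weeks, "how acceptable or unacceptable did you find the time it took to get the PrEP injection at your doctor's office". Items 8 to 11 use that window too, for the number of injections, remembering appointments, fitting injections into daily life, and hiding attendance at appointments. None of items 5 to 11 offers an answer for a participant who had no injection in the period.

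**Order within a month.** Figure 6a puts injection and survey in one cell at month 3: "Follow-up labs and 3 rd PrEP injection PRO data collection – Set #2 Persistence Assessment". Month 9 is laid out the same way. No order is stated. Section 6.2 has patients complete assessments in the app, and the text of Appendix F says tasks become available on set dates or when earlier tasks are done. No rule ties Set 2 to the injection.

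**The concern.** Items 5 to 7 ask about a discrete event, getting an injection, and the recall period is shorter than the interval between those events. If no injection falls in the period, item 5 is truthfully answered No by someone whose last injection hurt. That No is stored exactly like the No of someone whose injection was painless, and item 6 is never shown. Item 7 must be answered although there was no visit to rate.

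PrEP acceptance in CAB-LA versus oral PrEP is part of a stated secondary objective (section 3.3.2). The stored answers do not themselves show which kind of No was given. The same survey package does provide such answers elsewhere: Set 1 has one for no side effects in the last 4 weeks, and the baseline survey has a not-applicable option on rent.

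**Working it through.** The documents give no figure of their own to reproduce here; the check is date arithmetic.

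**Inputs**
- Injection months 0, 1, 3, 5, 7, 9, 11 (section 6.13.1).
- Set 2 months 3, 9, 12 (sections 6.2 and 6.14.1.3).
- Recall period: 4 × 7 = 28 days (Appendix B, Set 2).
- Assumption: one study month = 365.25 / 12 = 30.44 days, because the documents give no day counts.

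**Formula.** Gap = (survey month − month of the most recent earlier scheduled injection) × 30.44, compared with 28 days. The calendar range below comes from adding calendar months to every start date from 2023 to 2026.

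| Survey | Last earlier injection | Gap, average month | Calendar range | 28-day months | Gap minus 28, average month |
|---|---|---|---|---|---|
| Month 3, before that visit | Month 1 | 2 × 30.44 = 60.9 days | 59–62 | 56 | 32.9 |
| Month 9, before that visit | Month 7 | 2 × 30.44 = 60.9 days | 59–62 | 56 | 32.9 |
| Month 12 | Month 11 | 1 × 30.44 = 30.4 days | 28–31 | 28 | 2.4 |

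**Months 3 and 9.** Answered before the visit, the survey has no scheduled injection in its window for any start date. The earlier injection would have to be about 33 days late to fall inside. Answered after the visit and within 28 days of it, the survey captures that month's injection and the items work as written.

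**Month 12.** The gap exceeds 28 days for about 94% of start dates and is exactly 28 for about 6%. The margin is thin: a month-11 injection 3 or more days late, or a survey 3 or more days early, brings the injection inside. Sections 6.2.6 and 6.2.7 themselves foresee injections seven or more days late; at seven days the gap is 30.4 − 7 = 23.4 days.

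**Missed injection.** Section 6.6 treats PrEP as discontinued only after more than three consecutive missed months. A participant who misses month 11 may therefore still be surveyed at month 12, with the last injection 3 × 30.44 = 91.3 days earlier.

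**Which items depend on an injection in the window**
- Clearly: 5 and 7. Item 6 is reached only through a Yes on item 5.
- Less cleanly: 8 to 11, which concern the burden of the regimen or of appointments and can still be rated after a fashion.
- Not in the same way: 2 to 4, since side effects can be present without a recent injection; 1, 12, 15 and 16, which concern PrEP or medicines in general; 13 and 14, which concern the future.

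**The case against.** Three stronger readings are tempting, and the documents do not support them.

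1. *A reader might infer that no injection can fall in the month-12 window.* The nominal margin is 2 to 3 days, it vanishes with 28-day study months, and ordinary lateness that the plan expects reverses it.
2. *A reader might infer that most of the injection questionnaire has nothing to refer to.* Item 2 covers any side effects in the period, item 6 is skipped rather than answered blindly, and items 8 to 10 describe a regimen that the participant still knows.
3. *A reader might infer a bias in favour of CAB-LA.* Injection pain has no counterpart in the oral form (Appendix C). No scoring rule says what a skipped item contributes. Item 6 is answered only by those who report pain, so its direction is unclear. Section 7 names no between-arm test for acceptance.

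The defence can add that Figure 6a lists the injection ahead of Set 2 in the month-3 and month-9 cells, so the intended order may be visit first. It can also point out that Set 1 asks how bothersome side effects are, at months 1, 5 and 11, all injection months. Both are fair. But the listing does not bind the app, and the Set 1 item concerns side effects in general, not pain at the injection or its acceptability. The primary endpoints are untouched.

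What survives is narrower: the plan, followed as written, can collect a No that has two meanings.

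**Conclusion.** The mismatch between recall period and injection interval stands, limited to the injection-event items of one secondary patient-reported outcome. At month 12 it turns on a few unspecified days around a nominal gap of about 30 days. At months 3 and 9 it arises only if the survey precedes the visit, and then it is certain on schedule (about 61 days against 28).

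The supported consequence is that injection-pain acceptance may be under-recorded, because an ambiguous No also removes the follow-up item. How often this would happen cannot be computed, since the documents give neither survey windows nor the order of survey and visit. Neither size nor direction of any effect on the comparison with oral PrEP is established.

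The conclusion rests on reading 4 weeks as 28 days and on the text of Appendix F, whose screenshots were not available for this check. It is worth correcting because the repair is cheap, not because the main results depend on it.

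**What to change.** **Wording.** Anchor items 5 to 7 to *your most recent PrEP injection*. Alternatively, keep the wording and add *no injection in the past 4 weeks* as an answer to the injection items. Items 8 to 11 keep the 4-week frame in either case, since a single-injection anchor does not suit a question on the number of injections. The anchor retains more information at month 12, where many on-schedule participants would otherwise have to choose the new answer.

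**Release.** Open the month-3 and month-9 Set 2 task once that month's injection is recorded. Add a date fallback and the 'no injection' answer for participants who miss it. This step cannot help at month 12, where only the wording or the added answer does.

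**Reporting.** Keep the injection date and the survey date, and report the interval and the number choosing 'no injection'.

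**Cost.** Survey text and an app setting, with some means of telling the app that the injection was given, since Appendix E lists only surveys and assessments as app activities. The questionnaire, already modified, moves slightly further from its source. Anchored items lose the 4-week frame shared with the oral form, and recall lengthens for participants who have stopped injections. Treatment and visits do not change.
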